1.3 Schedule of Activities (SoA)

Study Period	Screening	Baseline / Randomization	Intervention				Follow-up TC ^a	Disc ^c	Notes
			TC	TC	3	4			
Visit	1	2	TC	TC	3	4	-	NA	
Scheduled Day	-14 to -1	1	7	21	42	84	98	NA	
Scheduling Window (recommended)	NA	NA	+3 days	±3 days	±4 days	±4 days	+7 days	NA	
Scheduled Week	-2 to -1	-	1	3	6	12	14	NA	
Administrative Procedures									
Informed Consent	X								
Informed Consent for FBR	X								FBR is optional for the participant.
Participant Identification Card	X	X							Update with allocation number once randomized.
Inclusion/Exclusion Criteria	X	X							
Demographics, Medical History	X								
Prior/Concomitant Medication Review	X	X	X	X	X	X	X	X	
Randomization		X							
Gefapixant/Placebo Administration/Dispensing		X			X				
Study Intervention Accountability					X	X		X	
Contact IRT System	X	X			X	X		X	
Efficacy Procedures									
Activate ePROs	X	X			X	X		X	See ePRO vendor manual.
Issue/instruct on use of e-Diary	X								
Review e-Diary compliance and instructions for use		X	X	X	X	X		X	Disc: Only when participant discontinues from study intervention (not discontinues from study).
Deactivate/collect e-Diary						X		X	Disc: Only when participant discontinues from study (not just discontinues study intervention).

Study Period	Screening	Baseline / Randomization	Intervention				Follow-up TC ^a	Disc ^c	Notes
			TC	TC	3	4			
Visit	1	2	TC	TC	3	4	-	NA	
Scheduled Day	-14 to -1	1	7	21	42	84	98	NA	
Scheduling Window (recommended)	NA	NA	+3 days	±3 days	±4 days	±4 days	+7 days	NA	
Scheduled Week	-2 to -1	-	1	3	6	12	14	NA	
LCQ		X			X	X		X	Complete at clinic visit: - Visit 2: After confirming eligibility for randomization and before first dose of study intervention. - Visits 3 & 4/Disc: Before all other procedures.
CSD	Complete daily (in evening)								Remind participant of need to complete daily.
Cough Severity VAS	Complete at Visit 1 clinic visit and daily (in evening)								Visits 2 & 3: Remind participant of need to complete daily.
PGIC						X		X	Complete at clinic visit.
WPAI		X				X		X	Visit 2: Complete at clinic visit before first dose of study intervention.
Safety Procedures									
Chest Radiograph or CT Thorax	X								Not required if done in the past 1 year and after onset of chronic cough.
Physical examination	X					X		X	Visit 1 (Screening): full examination. Visit 4 and Disc: directed examination.
Height	X								
Weight	X					X		X	
Vital Signs	X	X			X	X		X	
12-lead ECG	X								
Spirometry	X								

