A participant will be considered for inclusion in the assessment of an efficacy endpoint if the CSD and Cough Severity VAS are completed on at least 4 days during the 7-day period prior to a post-Baseline visit (other ePROs are completed at the clinic visit only). All efficacy analyses will be conducted based on the observed data only. No imputation is planned for the missing diaries or missing questionnaire items. The pattern of missing is assumed to be missing at random (MAR). The missing pattern will be inspected to determine if the MAR assumption is met. Sensitivity analyses will be implemented to explore the impact of departures from the assumption made in missing diaries.

The longitudinal ANCOVA model (aka. LDA method) assumes that data are missing at random. In this study, it is expected that missing at random and missing completely at random (MAR/MCAR) mechanisms will underlie most of the missingness, and the proportion of data missing not at random (MNAR), driven solely by unobserved values of the study endpoints, will be small.

In addition to the analysis approach specified in the above mentioned primary efficacy endpoint analysis section, the following sensitivity analyses will be used to assess the robustness of the primary analysis approach.

Tipping-point Multiple-imputation Analysis

The Variant 3 of the tipping point as described in paper [Ratitch et al. 2013] will be used. In that approach, missing data are first imputed for all visits under the MAR assumption, and then the worsening/shift is applied. This is repeated with increasing the delta-shift (worsening) until the result is no longer statistically significant. Specifically, for a given constant, c , the tipping point analysis is conducted in a fashion similar to that used in standard multiple imputation, whereby m ($=100$) complete datasets are randomly generated using the original observed dataset. These m complete datasets are subsequently analyzed using the primary model, and the results of those analyses are then combined. The construction and analysis of these m ($=100$) datasets requires four primary steps:

- 1) Using a Markov Chain Monte Carlo method, make the observed dataset monotone-missing. This will be accomplished for each treatment group using “proc mi” within SAS 9.3 or higher by utilizing the options “mcmc chain=multiple impute=monotone;”, in conjunction with all of the covariates (excluding treatment)

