included in the primary analysis model. The random seed will be set equal to 72644243. This step will generate m monotone-missing datasets.

- 2) Applying parametric regression to the monotone-missing datasets, impute all the missing values. This will be accomplished for each treatment group using “proc mi” within SAS 9.3 or higher utilizing the option “monotone reg”, in conjunction with all of the covariates (excluding treatment) included in the primary analysis model. The random seed will be set equal to 72644243. This step will generate m complete datasets.
- 3) To implement the tipping-point aspect of the procedure, subtract a constant c from each of the imputed values of the active arms (to the detriment of active).
- 4) Analyze each of the post-imputation complete datasets using the primary model, obtaining point estimates for the mean of interest (e.g. change-from-baseline treatment difference at 12 weeks) and the associated variance.

Using “proc mianalyze” within SAS 9.3 or higher, the $m=100$ means and variances from the m analyses will be combined to obtain the final test statistic and p-value (Rubin, 1987). The final test statistic $\bar{Q} / (T^{-1/2})$ is approximately distributed as t_v , where \bar{Q} is the sample mean of the m treatment difference estimates, $T = \bar{U} + (m+1) (B/m)$, \bar{U} is the sample mean of the m variance estimates, and B is the sample variance of the m treatment difference estimates. The degrees of freedom, v , will be computed as follows [Barnard and Rubin, 1999]: $v = [(v_1)^{-1} + (v_2)^{-1}]^{-1}$, where $v_1 = (m-1) [1 + (\bar{U}/(1+m^{-1}) B)]^2$ and $v_2 = (1-\gamma) v_0 (v_0 + 1) / (v_0 + 3)$, with $\gamma = (1+m^{-1}) B / T$ and where v_0 represents the complete-data degrees of freedom .

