3.9 SAMPLE SIZE AND POWER CALCULATIONS

The sample size calculations are powered to test the primary efficacy endpoint, with the following assumptions based on the results from a phase 2 chronic cough study. In MK-7264 Protocol 012, the change from baseline in LCQ total score at Week 12 was 1.1 and 1.7 for 20 mg and 50 mg compared to placebo. In this study, given the population is targeted for participants with recent onset chronic cough (< 12 months) which is different from participants with chronic cough (\geq 12 months) in Protocol 012, conservative assumptions were used for sample size calculation:

- Treatment difference in change from baseline in LCQ total score at Week 12 is 1.1 point
- Common SD of change from baseline in LCQ total score is 3.5

Based on the assumptions above, a total of 414 participants (207 participants per intervention group) will provide at least 80% power. The calculation is based on an overall one-sided $\alpha=0.025$ significance level, adjusted for one IA for efficacy ($\alpha=0.001$), and one final efficacy analysis ($\alpha=0.024$). A dropout rate of 15% at Week 12 is accounted for the sample size calculation to ensure 352 evaluable participants complete the Week 12 evaluation.

With assumptions on the AE rates in the placebo group based on the Protocol 012 results, the minimum detectable AE rate differences are 8.4%, 9.0%, and 7.7% in overall taste-related AEs, oral paresthesia AEs, and oral hypoesthesia AEs, respectively.

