4. APPENDICES

4.1 Model Specification, Assumptions, and Sample SAS Implementation Codes for the Primary Efficacy Analysis

Model

Let Y_{ijt} denote the measurement for subject i , with treatment assignment j , at time t . Here $j = 0, 1$ represent Placebo and MK-7264 45 mg BID, respectively. Also, $t = 0, 1, 2$ represent Baseline, visits at Week 6 and 12, respectively.

The longitudinal ANCOVA model, that is, a mixed linear model will treat percent change from baseline in measurement, $(Y_{ijt} - Y_{ij0})/Y_{ij0}$, as the dependent variable, and adjust for the following independent variables:

- baseline measurement Y_{ij0}
- treatment (categorical variable with 2 levels, Placebo and MK-7264 45 mg BID)
- week (categorical variable with 2 levels, 6, 12)
- Gender (males and females)
- the interaction of treatment by week

Observations across subjects are assumed to be independent. Post-baseline measurements within the same subject are assumed to follow multivariate normal distribution with mean vector as specified above and an unstructured covariance matrix.

This longitudinal model provides valid statistical inference in the presence of possible missing data if the missing data mechanism is ignorable (or more specifically, MAR or MCAR). This missing data mechanism requires that the probability of a data point being missing does not depend on the missing data after adjusting for the observed data.

Reasons for discontinuation from the trial may include lack of efficacy, clinical or laboratory adverse experiences, relocation, withdrawal of consent, protocol deviations, and/or data processing issues. Missing data caused by relocation and data processing issues, are likely to be MCAR. On the other hand, missing data caused by discontinuation due to lack of efficacy may belong to MAR because the discontinuation may depend on the observed efficacy outcomes. The MAR or MNAR mechanisms might each underlie the other reasons to some extent. If treatment in large part determines the loss of data for these other reasons (such as clinical or laboratory adverse experiences), the mechanism may be close to MAR since treatment assignment is an observed variable and included in the analysis model. Based on the prior trial results, missing data due to other reasons is relatively infrequent.

Model Convergence

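### The LCQ imputation models leave out the daily diary scores, so the MAR argument for lack-of-efficacy dropout before Week 6 has no post-baseline outcome behind it; adding a few diary means is a cheap improvement

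*Combined protocol and SAP*

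**What the plan says.** The primary model (protocol 9.6.1, sSAP 3.6.1) contains arm, visit, arm by visit, gender and baseline LCQ. sSAP 4.1 gives it two post-baseline visits, Weeks 6 and 12.

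The tipping-point analysis (sSAP 3.6.1, steps 1 and 2) imputes separately by arm, "in conjunction with all of the covariates (excluding treatment) included in the primary analysis model". Step 1 of the jump-to-reference (J2R) analysis likewise takes its covariates from the primary model. Neither lists a VAS or CSD variable.

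sSAP 4.1 gives two reasons for accepting MAR. The first is that "missing data caused by discontinuation due to lack of efficacy may belong to MAR because the discontinuation may depend on the observed efficacy outcomes". The second covers losses for other reasons, such as adverse experiences: these may be close to MAR because treatment is observed and is in the model. The same section concedes that MNAR may operate to some extent.

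On checking the assumption, sSAP 3.6.1 says: "The missing pattern will be inspected to determine if the MAR assumption is met".

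The protocol has participants complete VAS and CSD every evening from Visit 1 (Schedule of Activities; 8.2.1.2; 8.2.1.3).

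**The concern.** MAR is a statement about what the model conditions on. Dropout that depends on an observed outcome is ignorable only if that outcome is in the model. For a participant who leaves the study before Week 6, nothing observed after baseline is in it, so the imputed Week 12 value rests on baseline LCQ and gender within arm. The evening diary scores, which would show a poor early response, are left out.

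If such dropout is more common in one arm, that arm's imputed Week 12 mean is too high by more than the other's, and the gap passes into the treatment difference. This affects the c = 0 starting point of the tipping-point analysis, the MAR-imputed control arm of J2R, and the MAR estimate from the primary model. The sentence on inspection suggests that the assumption will be verified, which observed data cannot do.

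**Working it through.** **Scale from the plan (sSAP 3.9).** Difference 1.1, SD 3.5, 207 per arm, 15% dropout, final one-sided alpha 0.024.

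- Evaluable: 414 × 0.85 = 351.9, matching the stated 352 (176 per arm).
- Standard error: 3.5 × √(2/176) = 0.373.
- Power: Φ(1.1/0.373 − 1.977) = 83.4%, consistent with at least 80%. The sample size is not in question.
- Expected without a Week 12 value: 414 − 352 = 62, about 31 per arm. The documents do not say how many leave before Week 6, how they split by arm, or why they leave.

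**Bias in one arm.** Arm bias = share leaving early × (mean imputed value of leavers − their mean true value). Assumptions, none from the documents: odds of leaving before Week 6 rise by a factor e per SD of poorer early diary response; correlation of baseline LCQ with Week 12 change −0.3, and with diary response −0.2. Upward bias in LCQ points when imputing from baseline only:

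| Early dropout in the arm | r = 0.3 | r = 0.5 | r = 0.7 |
|---|---|---|---|
| 5% | 0.040 | 0.074 | 0.106 |
| 10% | 0.076 | 0.141 | 0.201 |
| 15% | 0.112 | 0.206 | 0.299 |

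Here r is the correlation between early diary response and Week 12 LCQ change. With the diary score in the imputation model, the bias is 0.001 or less in every cell.

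**Bias in the difference.** This is the gap between the arms' biases. Take 20% and 10% dropout (15% overall) with three quarters of it early: 15% and 7.5% leave before Week 6. Interpolating the 5% and 10% rows gives 0.058, 0.108 and 0.154 for the 7.5% arm. The gaps are 0.112 − 0.058 = 0.05, 0.206 − 0.108 = 0.10 and 0.299 − 0.154 = 0.15.

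**Simulated trials.** These used 207 per arm, true difference 1.1, SD 3.5, three quarters of dropout early and log-odds +1 per SD of poorer response. Ranges reflect different choices for the remaining unstated correlations. Bias in gefapixant minus placebo under LCQ-only MAR:

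| Dropout, gefapixant / placebo | r = 0.3 | r = 0.5 | r = 0.7 |
|---|---|---|---|
| 20% / 10%, all response-driven | +0.05 to +0.08 | +0.10 to +0.13 | +0.15 to +0.17 |
| 15% / 15%, all response-driven | about 0 | about 0 | about 0 |
| 10% response-driven in each arm, plus 10% unrelated to response on gefapixant | about 0 | about 0 | about 0 |
| 7% response-driven plus 10% unrelated / 13% response-driven | −0.03 | −0.07 | −0.10 |
| 10% / 20%, all response-driven | −0.05 to −0.06 | −0.10 to −0.11 | −0.15 to −0.16 |

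One early diary variable in the imputation brings the bias to about 0 and does not materially worsen precision.

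**Inspection.** A pattern of missingness can show who left, when, and how leavers compared on recorded data. It cannot show whether leaving also depended on the unrecorded Week 12 value, because MAR and MNAR mechanisms can produce the same observed data.

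**The case against.** **The bias is small and its sign is open.** The largest simulated value, 0.17, is under half a standard error (0.17/0.373 = 0.46). A reader might infer that the bias must favour gefapixant, because taste effects could raise dropout on that arm. The documents do not support this. Protocol 4.3 describes efficacy and dysgeusia as both rising with dose, and nothing links taste-driven dropout to poor response. If the gefapixant excess is unrelated to response, the bias is about 0; if more placebo non-responders leave, it favours placebo. This part of the objection stands.

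**The existing sensitivity analyses already guard against it.** In the 20%/10% case, J2R gives roughly 0.80 × (1.15 to 1.27) = 0.92 to 1.02, below the true 1.1. In the tipping-point analysis, a shift of 0.17/0.20 = 0.85 on gefapixant's imputed values absorbs the largest bias. This stands for bias toward gefapixant. With the split reversed, J2R gives 0.90 × (0.94 to 1.05) = 0.85 to 0.95, further from 1.1, and step 3 also moves gefapixant down. Both analyses answer different questions from a better-informed MAR estimate, and c is counted from the LCQ-only start.

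**Alignment.** Using primary-model covariates makes c = 0 mirror the primary analysis. That is a fair reason to keep the LCQ-only run, but not to omit a second one.

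**Scope.** A reader might infer that the gap covers anyone who leaves before Week 6. It does not. sSAP 4.1 has the separate, treatment-based reason for losses such as adverse experiences, and imputing by arm preserves it. Nor is stopping treatment the same as leaving the study (protocol 7.1): off-treatment data are used, and protocol 8.2.1 encourages completing the ePROs at remaining visits. However, footnote c of the Schedule of Activities and 8.10.3 limit those visits to adverse events, concomitant medications and e-Diary assessments without naming the LCQ, so these passages should be reconciled.

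**Discontinuation-visit LCQ.** A reader might infer that it is discarded and should become an auxiliary variable. The documents do not exclude it; they give no rule mapping it to Week 6 or 12. When discontinuation happens at a scheduled visit, it falls on that week. It would also be a poor auxiliary, since treatment completers never have one.

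**Conclusion.** The point holds as a cheap improvement, not as a flaw that undermines the trial. Both imputation models omit the diary scores. For participants who leave the study before Week 6 for lack of efficacy, the sSAP's own MAR argument therefore has no post-baseline outcome in the model.

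In the 20% versus 10% scenario the bias is about 0.05 to 0.17 points (5% to 15% of 1.1) in favour of the arm with more response-driven early dropout. It is about 0 when that dropout is equal. These sizes rest on assumed dropout rates, timing, selection strength and correlations, none of which the documents give.

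A reader might also infer that the change would correct the primary result. It would not: the primary model is untouched, and the gain is a better-informed check beside it. Separately, and without any simulation, inspecting missingness cannot establish MAR.

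**What to change.** - In tipping-point steps 1 and 2, and in the J2R parameter model where feasible, add a small set of pre-dropout diary means as auxiliary variables. For example, use mean change in VAS, with or without CSD, over Weeks 1-3 and 4-6. Use them in the imputation step only, not as covariates in the analysis model.
- Report the c = 0 result with auxiliaries beside the primary MAR estimate, and keep the LCQ-only c = 0 run for alignment with the primary model.
- Replace the inspection sentence with a commitment to describe missingness by arm, timing and reason.
- State how a Discontinuation-visit LCQ is mapped to Week 6 or Week 12. Also state whether participants with neither value are imputed, since sSAP 3.5.1 requires a post-baseline measurement for inclusion in the endpoint analysis.

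Cost: some extra programming, a slightly larger imputation model, and one c = 0 result that no longer mirrors the primary model exactly. No new data are needed, and the primary model, alpha and sample size do not change.

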Interim Analyses	
One planned IA will be performed in this study to examine the futility and efficacy. Results will be reviewed by the DMC. The IA is summarized below. Details are provided in Section 9.7.
 
 • Timing: To be performed when approximately 40% of participants (approximately the first 166 randomized participants) have either completed the study or discontinued the study intervention early. • Testing: Futility and Strong Benefit (Efficacy) analysis based on the primary endpoint of LCQ change from baseline in total score at Week 12 will be provided.
Multiplicity	
Since there is only one hypothesis (for the primary endpoint), no multiplicity adjustment is planned other than the IA alpha adjustment to the primary efficacy endpoint.

Sample Size and Power Calculations	
The planned sample size is 414 participants (207 per treatment group) for comparing the primary endpoint of LCQ change from baseline in total score at Week 12, assuming a pooled SD of 3.5 points. This sample size will detect a treatment difference of 1.1 points or more with at least 80% power at an overall one-sided 0.025 alpha level, adjusted for the IA ($\alpha=0.001$) for strong benefit and the final analysis ($\alpha=0.024$). This sample size accounts for a 15% dropout rate, targeting for 352 evaluable participants at Week 12. The details are described in Section 9.9.

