3.6 STATISTICAL METHODS

Statistical testing and inference for efficacy and safety analyses are described in Sections 3.6.1 – Statistical Methods for Efficacy Analyses and 3.6.2 – Statistical Methods for Safety Analyses, respectively. Unless otherwise stated, all statistical tests will be conducted at an overall significant level of 0.05 (2-sided).

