3.6.1 Statistical Methods for Efficacy Analyses

The analysis of efficacy endpoints will be based on the FAS population. Unless otherwise specified, analyses will include all follow-up efficacy data collected for those participants who discontinued treatment.

Primary Efficacy Analysis

The LCQ is collected at baseline and after administration of the study intervention at Weeks 6 and 12. The primary efficacy endpoint of this study is the LCQ change from baseline in total score. The primary analysis approach will be conducted utilizing the longitudinal ANCOVA model. In this model, the response vector consists of the LCQ change from baseline in total score at each post-Baseline visit. The model will include factors for intervention group, visit, interaction of treatment by visit, gender, and the baseline LCQ score. The model will use all available LCQ change from baseline in total score at Weeks 6 and 12. Contrasts will be constructed to compare the Gefapixant intervention group to the Placebo group at Week 6 and Week 12. The least squares mean change from baseline with the associated standard errors will be displayed for each intervention group. Overall estimated treatment differences (Gefapixant – Placebo) along with corresponding p-values and 95% CIs will also be presented, with the exception of the primary efficacy endpoint, in which the CI width will be adjusted for an IA.

Secondary Efficacy Analysis

The secondary efficacy endpoint will be analyzed using a similar longitudinal ANCOVA model as used for the primary efficacy analysis. The model will include terms for intervention group, visit, interaction of treatment by visit, gender, and baseline score.

[Table 1](#) summarizes the analysis strategy of the primary and secondary efficacy endpoints.

Table 1 Analysis Strategy for Key Efficacy Endpoints

Endpoint/Variable (at Week 12)	Statistical Method	Missing Data Approach
Primary		
Change from baseline in LCQ total score	Longitudinal ANCOVA	Model-based ^a
Secondary		
Change from baseline in Cough Severity VAS score	Longitudinal ANCOVA	Model-based ^a
ANCOVA = analysis of covariance; LCQ = Leicester Cough Questionnaire; VAS = Visual Analogue Scale		
^a Includes data collected after early intervention discontinuation.		

Exploratory Efficacy Analysis

- **CSD Total Score**

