This procedure will be repeated (using the same m imputed datasets) until the smallest c is found such that the significant result turns non-significant (i.e., $p > 0.05$). This tipping point value c provides a measure of robustness of the primary result. A relatively large value of c implies better robustness of the primary analysis against the impact of missing data in the study. It is noted that when $c=0$ the tipping point analysis described above corresponds to an analysis conducted under the assumption that the missing data are MAR. For values of c larger than 0, the tipping point analyses do not assume that the missing values follow a MAR mechanism. In fact, the analysis is based on a special MNAR mechanism in which all missing data across the arms are assumed to have a worse response by a constant amount of c than the values would have had under MAR.

Jump-to-reference (J2R) Multiple-imputation Analysis

J2R imputation falls under the category of pattern mixture models known as reference-based imputation (RBI). The RBI approach uses different imputation models for missing data in different treatment groups. In J2R, missing data in the control group are imputed under the MAR assumption, while missing data in the treatment groups are imputed under a MNAR assumption using the control group profile for time points after withdrawal.

The following steps will be used to implement the J2R multiple-imputation analysis.

- 1) A parameter-estimation model is fitted using PROC MCMC. All the covariates included in the primary analysis will be used for the parameter-estimation model. For the MCMC procedure, an initial random seed=72644243 will be used. N=500 sets of pseudo-independent samples of the model parameters will be drawn from the joint posterior distribution.

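### The tipping-point search ends at p > 0.05, a looser level than the primary test must meet, so c can only be equal or too large: trivially at the final analysis, more after an unlikely interim efficacy stop

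*Combined protocol and SAP*

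**What the plan says.** In the tipping-point analysis (sSAP 3.6.1), missing values are imputed under missing at random. A constant c is then subtracted from the imputed active-arm values (step 3) and the primary model is refitted. The search continues "until the smallest c is found such that the significant result turns non-significant (i.e., $p > 0.05"). The resulting c is presented as a measure of how robust the primary result is.

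The level for the primary test is set elsewhere. Protocol 9.1 states "at least 80% power at an overall one-sided 0.025 alpha level". sSAP 3.9 gives the split: "adjusted for one IA for efficacy ($\alpha=0.001$), and one final efficacy analysis ($\alpha=0.024". Protocol 9.9 has the same split.

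The primary confidence interval follows the split. sSAP 3.6.1 gives 95% intervals "with the exception of the primary efficacy endpoint, in which the CI width will be adjusted for an IA", and protocol 9.6.1 agrees. sSAP 3.6 adds that, unless otherwise stated, "all statistical tests will be conducted at an overall significant level of 0.05 (2-sided").

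Nothing in the public text carries the adjusted level into the tipping-point rule.

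**The concern.** A tipping value should be the shift at which the trial's own claim of success is lost. Here, significant means two-sided p of at most 0.048 for the primary test at the final analysis, but at most 0.05 for the search that probes that test. A shifted dataset with p = 0.049 would fail the primary criterion yet still count as significant in the search.

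The direction is fixed. Any c that gives p above 0.05 also gives p above 0.048 (and above 0.002), so the first c to cross 0.05 cannot come before the first to cross the stricter level. The mismatch can only flatter the result. At stake is how c is read in the study report. The primary test itself is not affected.

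**Working it through.** **Inputs from the documents**
- One-sided alpha 0.001 (interim) and 0.024 (final): protocol 9.1 and 9.9, sSAP 3.9.
- Difference 1.1 and SD 3.5: sSAP 3.9.
- 414 randomized 1:1, 15% dropout, 352 evaluable (176 per arm): sSAP 3.9.
- About 141 completers at the interim (70.5 per arm): protocol 9.7.1, sSAP 3.7.1.
- Shift on imputed active-arm values only: sSAP 3.6.1, step 3.

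**Assumptions.** The missing fraction d in the active arm is 15%, with a range shown. A normal approximation is used, with the standard error taken from the evaluable number.

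**1. The plan's own figures.** 0.001 + 0.024 = 0.025. 414 × 0.85 = 351.9, or 352. SE = 3.5 × √(2/176) = 0.3731. Power at one-sided 0.024 is Φ(1.1/0.3731 − 1.9774) = Φ(0.971) = 83.4%, consistent with the stated minimum of 80%.

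**2. Thresholds.** Doubling the one-sided levels gives two-sided 0.048 and 0.002. The critical values are 1.9600 (0.05), 1.9774 (0.048) and 3.0902 (0.002).

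**3. Formula.** A shift c on a fraction d of the active arm lowers the treatment difference by about d × c. The tipping value is therefore c = (difference − z × SE)/d, and the overstatement is (z_strict − 1.9600) × SE/d.

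**4. Final analysis.** (1.9774 − 1.9600) × 0.3731 = 0.0065 LCQ points in the difference. Dividing by d:

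| Missing fraction d | Overstatement of c (LCQ points) |
|---|---|
| 5% | 0.130 |
| 10% | 0.065 |
| 15% | 0.043 |
| 20% | 0.032 |
| 25% | 0.026 |

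With an observed difference of 1.1 and 15% missing, c is (1.1 − 0.731)/0.15 = 2.46 at 0.05 and (1.1 − 0.738)/0.15 = 2.41 at 0.048, a change of 1.8%.

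**5. After an efficacy stop at the interim.** SE = 3.5 × √(2/70.5) = 0.5895, and (3.0902 − 1.9600) × 0.5895 = 0.666 points in the difference.
- 141 evaluable, 15% missing: 0.666/0.15 = 4.4 points.
- 141 evaluable, 40% missing (assumed): 0.666/0.40 = 1.7 points.
- 352 evaluable (assumed), 15% missing: 1.1303 × 0.3731 = 0.4217, and 0.4217/0.15 = 2.8 points.

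A missing fraction below the plan's own 15% allowance would give more (6.7 points at 10%), but that is hard to expect after a stop in which all participants are discontinued.

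An efficacy stop needs an observed difference of 3.0902 × 0.5895 = 1.82. Its probability under the design assumptions is Φ((1.1 − 1.82)/0.5895), or about 11%.

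**6. Simulation check.** A multiple-imputation simulation used 100 imputations, Rubin's rules with Barnard–Rubin degrees of freedom, 15% missing and an assumed Week 6/Week 12 correlation of 0.6.
- Final analysis: median overstatement 0.041 points (range 0.037 to 0.044). The tipping value was unchanged in 92% of runs on a 0.5-point grid and in 63% on a 0.1-point grid.
- Interim-sized dataset with 15% missing: median 4.1 points (range 3.5 to 4.6).

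**7. Is 0.05 recoverable?** With 40% information at the interim, the additive split gives an overall one-sided error of 0.0244. Spending the full 0.025 would allow about 0.0492 two-sided at the final analysis. That is still below 0.05, and the stated level is one-sided 0.024.

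**The case against.** The best defence is that the tipping-point analysis is supportive, spends no alpha, and has no pass/fail rule: the sSAP says only that a larger c means more robustness. The general statement in sSAP 3.6 also sets 0.05 two-sided for tests unless otherwise stated, and using that familiar level for a descriptive measure is not unreasonable. The plan states no grid for c, so the step size could matter more than 0.048 versus 0.05.

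The point about materiality stands for the final analysis. The appeal to sSAP 3.6 does not settle the matter, because the 0.05 there is the overall level across both looks, not the level of one p-value at the final analysis.

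A reader might go further in four ways that the documents do not support:
- **A shifted result at p = 0.04 after an interim stop would be declared robust.** The plan declares nothing robust at any p-value.
- **c would be 4.4 points too large after an interim stop.** This assumes exactly 141 evaluable and 15% missing. Protocol 9.7.1 and sSAP 3.7.1 also admit partial data from later participants. Protocol 9.7 includes data through close-out visits in the report, and protocol 4.4.1 says that all participants would be discontinued. More evaluable participants or a larger missing fraction both shrink the figure. The documents also do not say that the tipping-point analysis would be run after such a stop.
- **J2R uses a wrong threshold.** Its description states none.
- **The primary test's error rate is affected.** It is not.

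**Conclusion.** The mismatch and its direction are certain on the text: the tipping rule uses 0.05, while success at the final analysis requires two-sided 0.048. It is a minor inconsistency. At the final analysis c is overstated by about 0.04 LCQ points at 15% missing, on a scale from 3 to 21, and in practice often not at all. After an efficacy stop at the interim the overstatement could be roughly 2 to 4 points, conditional on that unlikely stop, on the analysis being run then, and on the assumed evaluable number and missing fraction.

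Three limits apply:
- The values 0.048 and 0.002 are doubled from the stated one-sided levels and are not printed, and the detailed interim decision criteria are not in the public text.
- The sizes assume that only the active arm is shifted, as in step 3. The closing sentence of the tipping-point text speaks of missing data in all arms being worsened. With similar missingness in both arms, the difference would barely move and these figures would not apply.
- The visit correlation, and missing fractions other than 15%, are assumptions.

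**What to change.** In sSAP 3.6.1, replace the parenthesis that defines non-significance as p > 0.05 with: *two-sided p exceeds the nominal level at which the primary hypothesis was declared significant (0.048 at the final analysis; the interim level, 0.002, if success was declared at the interim analysis)*. Add that the same level applies if the J2R result is described as significant or not.

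The cost is one phrase and one constant in the program. No new data, visits or models are needed. The reported c stays the same or becomes slightly smaller.
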